If, at any time, a subject develops or meets any of the exclusionary criteria, the subject will be removed from the study and receive the Standard of Care as prescribed by the primary investigator or designee.

If, at any time, the investigator determines the subject is no longer appropriate for study treatment or suitable for participation in the research trial, the subject will be removed from the study and receive the Standard of Care as prescribed by the primary investigator or designee.

Study Monitoring:

Prior to study start, IrriMax Corporation representatives will visit the investigator and facility to review the protocol and procedures to be followed for the IRR-CT-901-2013-01 study and confirm the facility's ability to conduct the study. This visit is known as the Site Selection Visit (SSV). Due to timing or confidence in the ability of an investigator and facility, the SSV may be combined with the SIV. Monitoring visits will be performed in relationship to site recruitment rates. The frequency of monitoring will coincide with recruitment rates, as

Study Number IRR-CT-901-2013-01	Version: 1.0	01AUG2014
© Confidential IrriMax Corporation		Page 26 of 35

defined in the monitoring plan, in order to confirm continuing compliance with regulatory standards, GCP, and protocol requirements.

The sponsor will designate a study monitor, or the study monitor of the designated CRO, will maintain contact with the investigator and designated staff by telephone, and/or letter, and/or email between visits. Monitoring visits to the investigational site will be conducted by the assigned monitor(s). Frequency will be contingent upon enrollment. The investigator will allow the study monitor to inspect the clinical facilities. The eCRF and subject's corresponding source documentation are to be fully available for review by the sponsor's representatives at regular intervals. These reviews verify adherence to study protocol and data accuracy in accordance with federal regulations. All records at the investigational site are subject to inspection by health authorities including the FDA. In accordance with International Conference on Harmonisation (ICH) E6 Section 6.10, source documents include, but are not limited to the following:

- Study specific source documentation
- Copies or transcribed health provider notes, certified for accuracy after production
- Recorded data from automated instruments such as (ECGs, rhythm strips, electroencephalograms (EEGs), pulmonary function tests, etc.)
- Records of telephone contacts
- Evaluations checklists
- Study Product distribution and accountability logs maintained by study personnel
- Correspondence between physicians or memoranda to IRBs/IECs regarding any subject's treatment

Statistical Methodology:

Endpoints

Efficacy

Primary

The primary efficacy endpoint is the rate of SSI observed within 30 days from the date of index operation.

Secondary

The secondary efficacy endpoints will include the following:

- The length of stay in the hospital
- Rate of readmission to the hospital, within 30 days from the date of the index operation
- Estimated costs of the index hospitalization

Exploratory Endpoints

The following outcomes will be reviewed as exploratory endpoints:

- Superficial surgical site infection (SSI)
- Deep surgical site infection (SSI)
- Organ/space surgical site infection (SSI)
- Ventilator associated pneumonia (VAP)
- Catheter associated urinary tract infection (CAUTI)
- Central line associated blood stream infection (CLABSI)
- Deep vein thrombosis (DVT)
- Pulmonary embolus (PE)
- Acute cardiac event

Study Number IRR-CT-901-2013-01	Version: 1.0	01AUG2014
© Confidential IrriMax Corporation		Page 27 of 35

- Clostridium difficile (C-diff) infection
- MRSA infection
- Mortality

Safety

The safety of the IrriSept irrigation unit will be assessed through the clinical review and analysis of adverse events.

Randomization

Subjects who meet all inclusion and exclusion criteria will be centrally randomized in the OR in a 1:1 ratio to either the study product group or the control group, in accordance with a computer-generated block randomization schedule prepared by a non-study statistician. A unique randomization number and associated treatment assignment will be made using an interactive web-based response system (IWRS). Randomization will be stratified by center with no center allowed to enroll more than 120 subjects.

Statistical Methods

This section outlines the statistical analysis strategy and procedures for the study. If, after the study has begun, changes are made to primary and/or key secondary hypotheses, or the statistical methods related to those hypotheses, then the protocol will be amended (consistent with ICH Guideline E-9). Changes to exploratory or other non-confirmatory analyses made after the protocol has been finalized, along with an explanation as to when and why they occurred, will be listed in the Clinical Study Report (CSR) for the study. Post hoc exploratory analyses will be clearly identified in the CSR. A separate Statistical Analysis Plan (SAP) with further details than presented here will be finalized prior to first patient enrolled to minimize any bias, as the study is non-blinded.

Power and Sample Size

The determination of sample size for this study is based on the primary objective to demonstrate the superiority of the IrriSept irrigation unit versus conventional standard of care in patients who undergo open abdominal laparotomy for abdominal trauma or acute surgical abdomen within 36 hours of initial presentation to their healthcare organization. The primary endpoint is the rate of SSI observed within 30 days (+/- 3 days) from the date of the index operation.

Based on historical data, it is assumed that the rate of SSI within the standard of care group will be \geq 20%. A total of 600 patients (300 per group) will provide \geq 90% power to demonstrate a reduction in the rate of SSI, up to 50%, assuming a control group rate for SSI of \geq 20%, based on a two-sided Chi-square test with a 5% significance level. The following table shows the power achieved under various combinations of control group SSI rates and relative treatment differences.

Table 2.1: Power associated with a total sample size of 600 (n=300/group), based on a two-sided Chi-square test with a 5% significance level.

Control Group SSI	Relative Treatment Difference (IrriSept/Control)		
Rate	50% Reduction	40% Reduction	30% Reduction
15%	83%	62%	38%
20%	93%	76%	50%
25%	98%	87%	61%

It is anticipated that approximately 1100 patients will be screened, 650 patients will be enrolled, to obtain 600 evaluable patients, based on a non-evaluable rate of approximately 5%. All calculations were carried out in SAS version 9.2 using the comparison for two independent proportions procedure in PROC POWER.

Study Number IRR-CT-901-2013-01	Version: 1.0	01AUG2014
© Confidential IrriMax Corporation		Page 28 of 35

Analysis Populations

Intention-to Treat (ITT)

The intention-to-treat population will be defined as all randomized subjects. Subjects will be assigned to a group based on the group they were randomized to.

Per-Protocol Population (PP)

Within the ITT population, subjects will be considered evaluable if they completed the 30 day follow up visit. Subjects who are withdrawn from the study prior to the 30 day follow up will be designated "non-evaluable" and excluded from the PP population.

Safety Analysis Set (SAS)

The safety analysis set will consist of all randomized subjects who underwent an emergency operation. The safety analysis set will be used for all safety analyses. Subjects will be assigned to a group based on the actual procedure received.

Efficacy Analyses

Primary Endpoint

For the primary endpoint, the number and proportion of patients with a SSI observed within 30 days from the date of emergency operation will be summarized by treatment group, along with the difference and 95% confidence interval for the difference (based on the Wald method). If a patient is missing their end of study assessment, or if they died prior to the end of study assessment, they will be classified as having met the primary endpoint of a SSI. A comparison between treatment groups will be made using the Cochran-Mantel-Haenszal test, stratified by site. The two-sided p-value, the adjusted relative risk (IrriSept/Control) and 95% confidence interval of the relative risk (based on the Wald method) will be reported. The study will be deemed successful if the two-sided p-value for the end of study treatment difference is < 5%.

It is anticipated that treatment groups will be well balanced with respect to baseline and demographic characteristics as well as risk factors for SSI, however if there are imbalances these will be accounted for in a supportive analysis using logistic regression. In these analyses, a logistic regression model with treatment as a fixed categorical variable and key baseline/demographic variables that are imbalanced will be included in the model to obtain adjusted estimates of the treatment effect in the form of odds ratios with two-sided 95% confidence intervals. Identification of variables to include will be based on comparisons between the two groups using appropriate two-sided tests based on the underlying distribution of the data. Those variables that are found to be significant (p < 0.05) will be included in the model.

Secondary Endpoints

The rate of readmission within 30 days from the date of the abdominal surgical procedure will be analyzed using the same methods as described for the primary endpoint.

The length of stay in the hospital will be calculated as the difference between the date of discharge and the date of admission, plus 1 day. Length of stay will be summarized by treatment group using descriptive statistics. As length of stay data tends to be highly skewed, a comparison of the LOS between the two treatment groups will be made by modeling the log LOS using a mixed effect model with a fixed effect term for treatment and a random component for center. This means and 95% confidence intervals for the difference between treatment groups will be back transformed and presented along with the two-sided p-value from a two-sample t-test.

An additional analysis will seek to define risk-adjusted length of stay outliers and whether there are observed differences between the two study populations. Using the post-operative length of stay as the dependent variable, a linear model will be used by employing those patients in the study who had no complications identified through the entire 30 day postoperative period. Again, hospital variables will be used. The observed length of stay for all patients will then be compared to the expected length of stay from the model to determine

Study Number IRR-CT-901-2013-01	Version: 1.0	01AUG2014
© Confidential IrriMax Corporation		Page 29 of 35

excess lengths of stay in the two groups of patients. A moving average control chart will then be used by methods previously published to identify length of stay outliers based upon the prediction model within each hospital.[22-24] For each hospital, the total predicted length of stay will be set equal to the total observed length of stay in the control chart computation. The 2- σ , 2.5- σ , and 3- σ outliers by this method will identify the worst complications and whether there are differences in occurrences between the two treatment groups. A summary of the number and proportion of outliers will be presented by treatment group.

To assess cost of care differences between the two study populations, the UB-04 will be used to provide the total hospital charges for each study subject. These charges will be converted to cost estimates by using the hospital all-payer cost-to-charge ratio.[25] Hospital cost for all patients in the trial without complications will be used to define the uncomplicated risk-adjusted cost of hospitalization for this study cohort. Hospital cost will be the dependent variable and stepwise forward regression will be used to define statistically significant independent variables. Hospital variables will be used. The determination of excess costs of care will then be determined at the hospital level. Total predicted costs will be set equal to total observed costs, and excess costs will be determined by subtracting (observed) – (predicted) for all patients. These cost excesses will then be summarized by treatment group using descriptive statistics, and a comparison between groups made using the Wilcoxon Rank Sum test.

Exploratory Analyses

Univariate assessment of categorical risk factors and of continuous risk factors will be assessed to identify whether differences exist between the two populations of patients in the frequency of independent variables following patient randomization. Risk factors with P<0.05 on univariate analysis will then be used to create a forward stepwise logistic regression model to predict SSI. Hospital dummy variables will be employed to remove hospital effects. Logistic coefficients will be defined for the clinical variables including the use of the IrriSept irrigation system. Odds ratios and confidence intervals will be established to evaluate statistical significance, or lack thereof, of the IrriSept system. An additional benefit of this modeling will be the development of risk equations that combine administrative, clinical, and laboratory data into the prediction of SSI in this population of patients.

Multiplicity

As there is a single primary endpoint, and no formal unblinded interim analyses that will utilize the primary endpoint to modify the trial, no adjustment for multiplicity is planned. No adjustment for multiplicity is planned for the analysis of secondary endpoints

Sub-groups

To determine whether the treatment effect is consistent across various subgroups, the estimate of the odds ratio (and 95% CI) for the primary endpoint will be estimated and displayed using forest plots for the following sub-groups:

- Age category (≤65 vs. >65 years)
- Gender (female, male)
- Emergency laparotomy for trauma exclusively vs. laparotomy for emergency general surgery

For the analysis of each sub-group, a logistic regression model for the primary endpoint will be used, with terms for treatment group, the sub-group and the sub-group by treatment interaction. The odds ratios and 95% CI's within each sub-group category will be reported, along with the p-value for the interaction term.

Safety Analyses

All safety analyses will be presented using the safety analysis set. No formal hypothesis testing will be conducted.

Adverse Events

Adverse events will be coded using MedDRA (Version 17.x). All AEs that occur after the start of surgery (cut time) will be summarized using frequency counts and percentages. Summaries will be presented by treatment

Study Number IRR-CT-901-2013-01	Version: 1.0	01AUG2014
© Confidential IrriMax Corporation		Page 30 of 35

group using the MedDRA level hierarchy (system organ class, high level group term, high level term, and preferred term) as follows:

- Overall (i.e., regardless of severity or relationship to treatment)
- By severity grade (mild, moderate, severe, or life threatening)
- By relationship to study product (potential relationship to study product or unlikely/no relationship to study product) according to the mapping scheme below:
 - o Potentially related: will include all AEs with a relationship rating of "definite", "probably" or "possibly."
 - Unlikely/not related: will include all AEs with a relationship rating of "unlikely" or "unrelated."

Unless otherwise specified, at each level of patient summarization in reporting the incidence of the AEs, a subject will be counted once if the subject reported one or more events. If more than one occurrence of an event is reported, the event of the worst severity or the worst-case relationship assessment will be summarized.

AEs leading to premature discontinuation and serious AEs (SAEs) will also be summarized by treatment group and relationship. AEs leading to premature discontinuation will be defined as any AE with an action taken equal to "permanently discontinued."

Demographics and Baseline Summaries

Demographic variables (e.g., age, gender, race, ethnicity) and baseline characteristics (e.g., medical history, PATI, AIS and ASA scores, adherence to SCIP prophylactic antibiotic-specific guidelines, surgical skin preparation used, shock, (systolic BP < 90 mm Hg), intubation, active infection, transfusion of blood/blood products, primary injury in trauma or primary organ(s) in the acute abdomen and intraoperative risk factors), will be summarized by treatment group. The comparability of the treatment groups for relevant demographic and baseline characteristics will be assessed by descriptive statistics. No statistical hypothesis tests will be performed. For continuous data, summaries will include the number of observations, mean, standard deviation, median, 25th and 75th quartiles, minimum and maximum values. For categorical data, frequency counts and percentages will be reported.

Concomitant Medications/Antibiotics

Concomitant medications are medications that are taken at any time after enrollment. Concomitant medications will be coded using the WHO Drug Dictionary and summarized by drug class and preferred term for each treatment group. The summaries will present the number and percentage of patients using each medication in each treatment group. Patients may have more than one medication per preferred term. At each level of summarization, a patient is counted once if he/she reported one or more medications at that level.

Disposition

A clear accounting of disposition including, the number and percentage of patients screened, randomized, and completed, as well as the primary reasons for screen failure and reasons for early discontinuation of therapy will be reported overall and by treatment group.

Subjects who withdraw from the study (either voluntarily or involuntarily) or do not complete the required End of Study visit will be designated as "non-evaluable." Any data collected on these subjects will not be used in the final efficacy analysis. For those who withdraw consent, screen fail information will be collected. For those subjects lost to follow-up will be noted in the database as early termination. Subjects who are classified as "non-evaluable" will be replaced to the extent required to enroll 600 evaluable subjects.

Study Number IRR-CT-901-2013-01	Version: 1.0	01AUG2014
© Confidential IrriMax Corporation		Page 31 of 35

Interim Analyses

An interim analysis is planned when approximately 33% and 66% of the total number of patients has been enrolled. The purpose of these interim analyses is to monitor safety and study conduct. At the second interim analysis, the sample size will be re-estimated using the conditional power approach.

All persons involved in the conduct and analysis of the study will remain blinded to the results of the interim analysis.

Test Material Compliance and Accountability:

An initial supply of Study Product will be supplied to the study site, by IrriMax Corporation, at least one (1) week prior to study commencement.

Procedures and instructions for Study Product dispensing and accountability will be provided in the Investigator Site Binder.

Investigator Site Responsibilities:

Study site personnel involved in the conduct of IRR-CT-901-2013-01 must read and demonstrate understanding of the protocol, source documents, case report forms and all other documentation required to enroll qualified subjects and complete the study documentation in an agreed timeframe.

Additionally, study site personnel who agree to conduct the study must complete required training (Site Initiation Visit) and agree to receive and properly account for study materials, including but not limited to:

- Study Product
- Study Materials

The study product and materials must remain in the study environment at all times during study conduct.

Study personnel are responsible for ensuring that documentation forms are properly completed. Lastly, study personnel must understand the study process for reporting and documenting Adverse Events (AEs) on the Adverse Event study log, to and on behalf of the sponsor as well as following any AE procedures in place at the facility.

Subjects' Responsibilities:

Subjects must agree to participate in the study as documented in the information contained in the ICF.

Subjects may discontinue their participation at any time during the study as per ICH GCP guidelines.

IrriMax Corporation Personnel Responsibilities:

IrriMax Corporation personnel will be on-site, when possible, to conduct a Site Initiation Visit to ensure study training of all study personnel.

Data monitoring will also be conducted by IrriMax staff or representative on-site. Frequency and total number of monitoring visits will be determined by recruitment rate and monitoring plan.

Appendices and other Study References:

Essential regulatory documents and other study-specific documents and forms will be provided to investigational sites in a comprehensive study reference binder.

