• To compare the rate of SSI in the IrriSept system randomization group to the rate of SSI in Standard of Care randomization group.

Secondary Objective(s):

- To compare the hospital readmission rate of subjects receiving the IrriSept system to the hospital readmission rate of subjects receiving Standard of Care treatment.
- To compare the estimated hospital cost to charge ratio between the IrriSept system and Standard of Care.
- To compare the length of hospital stay between IrriSept system and Standard of Care.

Study Product:

Product Name: IRRISEPT[™] Wound Debridement and Cleansing System

Registration Number: 3005706359

Product Status: Active

Registered Company: IrriMax Corporation

IrriSept system containing sterile 0.05% Chlorhexidine Gluconate (CHG) in water for irrigation, USP (99.95%), and sterile 0.9% normal saline packaged with 2 sterile IrriProbes, packaged for study use as a "kit". Two (2) complete "kits" will be used per the study specific IFU (Instructions for Use) for each subject randomized to Study Product.

Study Design:

This is a randomized, open-label, parallel-group study. The study consists of 3 parts: a Screening Phase typically performed in the Emergency Department, a randomized, open-label Treatment (Perioperative) Phase, and End of Study, a 30-day Follow-up.

Study Number IRR-CT-901-2013-01	Version: 1.0	01AUG2014
© Confidential IrriMax Corporation		Page 10 of 35

Study Sample Size:

1100 screened, approximately 650 completed, 600 evaluated

Study Background:

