This is a Phase IV, multi-center, prospective, randomized controlled, comparator clinical trial. Twelve to fourteen (12-14) Level I Trauma Centers throughout the United States will participate as research sites conducting this protocol. After the research site receives Institutional Review Board (IRB) approval, patients between the ages of 18-70 years old who undergo open abdominal laparotomy for abdominal trauma or acute surgical abdomen within thirty-six (36) hours of initial presentation to their healthcare organization may be eligible for study inclusion. Exclusion criteria includes: known allergy to chlorhexidine gluconate (CHG), Abbreviated Injury Scale (AIS) score of six (6), American Society of Anesthesiologists Physical Status Classification (ASA) score of five (5) or greater, female subjects who are pregnant and/or breast feeding, those patients undergoing a damage control laparotomy, a drain is placed within the wound or an intra-abdominal drain exits through the primary incision, reoperation occurs through the primary incision or transgresses the primary incision as the index procedure within 30 days, and those enrolled in a concurrent, ongoing interventional, randomized clinical trial.

Patient risk factors will be assessed at screening include chronic uncontrolled hypertension, chronic heart disease, chronic renal disease, chronic pulmonary disease, diabetes mellitus, HIV, chronic liver disease, a BMI of less than 18 or above 40, coagulopathy, current long-term steroid use, current smoker, and current cancer. Additional assessments include PATI (Penetrating Abdominal Trauma Index), AIS and ASA scores, and adherence to SCIP prophylactic antibiotic-specific guidelines. Other measures to be documented will include antibiotic used and surgical skin preparation used. The following present on admission (PoA) characteristics are documented: shock, (systolic BP < 90 mm Hg), intubation, active infection, transfusion of blood/blood products and primary injury in trauma or primary organ(s) in the acute abdomen. Intra-operative SSI risk factors including drains, staple versus sutures, surgical time (skin to skin), blood/blood products, and body temperature below 36°C are assessed and risk adjusted in the final analysis.

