Exploratory endpoints at study completion include: infection (superficial, deep, organ space), ventilator associated pneumonia (VAP), catheter associated urinary tract infection (CAUTI), central line associated blood stream infection (CLABSI), deep vein thrombosis (DVT), pulmonary embolus (PE), acute cardiac event, Clostridium difficile (C-diff) infection, MRSA infection, mortality and length of stay (LOS).

The Standard of Care (SoC) irrigation arm subjects receive routine surgical irrigation Standard of Care (SoC). It should be noted that routine SoC is at the sole discretion of the investigator and institution and may or may not involve surgical wound irrigation. If irrigation is used, it will be delivered by bulb syringe or pour method but not a pressure device, which can range from a syringe with a cannula to jet lavage.

STUDY DETAILS

Study Rationale/Purpose:

The primary objective of this study is to compare the rate of surgical site infections in the IrriSept system randomization group to the rate of surgical site infections in the Standard of Care randomization group. There are three secondary objectives:

- To compare the hospital readmission rate of subjects receiving the IrriSept system to the hospital readmission rate of subjects receiving Standard of Care treatment.
- To compare the estimated hospital cost to charge ratio between the IrriSept system and Standard of Care.
- To compare the length of hospital stay between IrriSept system and Standard of Care.

Inclusion Criteria:

- 1. Is male or female, 18 to 70 years of age,
- 2. Has provided written informed consent
- 3. Has experienced abdominal trauma, blunt or penetrating requiring open abdominal laparotomy with primary closure or acute surgical abdomen requiring open abdominal laparotomy with primary closure
- 4. Undergoes the required surgical procedure within 36 hours of presentation to the healthcare system.

Exclusion Criteria:

- 1. Known allergy to Chlorhexidine Gluconate (CHG)
- 2. Abbreviated Injury Scale (AIS) score of six (6)
- 3. American Society of Anesthesiologists Physical Status Classification (ASA) score of five (5) or greater
- 4. Female volunteers who are pregnant and/or breast feeding
- 5. Damage control laparotomy
- 6. Drain is placed within the wound or an intra-abdominal drain exits through the incision
- 7. Reoperation occurs through the same incision or transgresses the same incision as the index procedure within 30 days

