Subjects who withdraw from the study prior to Visit 2 will be considered non-evaluable and will not be followed beyond the point of withdrawal or termination from the trial. Evaluable subjects completing the trial will not be followed beyond 30 days for study purposes.

Assessments include:

- Subject status
- Documentation of any additional hospital admissions and surgeries
- Assessment of current Surgical Site condition
- Documentation of Surgical Site Infection (SSI)
- Recording of cultures, if SSI documented
- Documentation of any Adverse Events (AEs), Serious Adverse Events (SAEs), Adverse Device Effects (ADEs), Serious Adverse Device Effects (SADEs) and Unanticipated Serious Adverse Device Effects (USADEs)
- Documentation of all Antibiotic Concomitant Medications used post-operatively through Visit 2
- Recording of Protocol Deviations

Table 3: A schematic of all study procedures

IRR-CT-901-2013-01				
Schedule of Events	SCHEDULE OF EVENTS			
		Visit 1		Visit 2 / End Of Study
	SCREENING PHASE	PERI- OPERATIVE PHASE	POST SURGICAL PHASE / ET	30-DAYS POST PROCEDURE
Informed Consent/Assent (Subject/Surrogate/LAR)	X		X	
Demographics	Χ			
Inclusion/Exclusion Criteria Review	X	X	X	
Record Surgical Risk Factors	X			
Record Present on Admission Status	X			
Primary Injury for Penetrating Abdominal Trauma, if applicable			X	
Primary Injury for Blunt Trauma, if applicable			X	
Primary Injury for Acute Abdomen Surgery, if applicable	Χ		X	
Complete Abbreviated Injury Score (AIS)	Χ			
Complete Glasgow Coma Scale (GCS)	Χ			
Record Lab Results (serum and cultures) if applicable	Χ			
Record ASA Physical Status Classification System Score		X		
Subject Randomization, Study Drug Dispensing and Compliance		X		
Record Perioperative assessments		X		
Assess Presence of Surgical Site Infection (SSI)				X
Record SSI Risk Factors				X
Record Study Adverse Events and Serious Adverse Events	X	X	X	X
Record and Report Study Adverse Device Effect, Serious Adverse Device Effect, and Unanticipated Serious Adverse Device Effect (USADEs)		Х	Х	Х

Adverse Events (AEs), Serious Adverse Events (SAEs), Adverse Device Effect (ADEs), Serious Adverse Device Effect (SADEs), and Unanticipated Serious Adverse Device Effect (USADEs)

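### Removal for reoperation within 30 days takes randomised subjects out inside the endpoint window, and the plan gives two incompatible rules for analysing them

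*Combined protocol and SAP*

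**What the plan says.** **Removal.** The section headed Criteria For Removal From The Study gives no cut-off at randomisation. Its rule reads: "If, at any time, a subject develops or meets any of the exclusionary criteria, the subject will be removed from the study".

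**The criterion.** Exclusion Criteria, item 7: "Reoperation occurs through the same incision or transgresses the same incision as the index procedure within 30 days". The Protocol Synopsis repeats it: "reoperation occurs through the primary incision or transgresses the primary incision as the index procedure within 30 days".

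**Timing.** Under Randomization, eligible subjects are "centrally randomized in the OR in a 1:1 ratio". Under Endpoints: "The primary efficacy endpoint is the rate of SSI observed within 30 days from the date of index operation". Under Study Design: "This is a randomized, open-label, parallel-group study".

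**After removal.** Visit 2: End of Study says that subjects who withdraw before that visit "will be considered non-evaluable and will not be followed beyond the point of withdrawal or termination from the trial". Disposition makes clear that removal by the investigator counts: the sentence opens "Subjects who withdraw from the study (either voluntarily or involuntarily" and calls such subjects non-evaluable. It then keeps their data out of the final efficacy analysis and replaces them until 600 are evaluable.

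**Analysis.** Analysis Populations defines ITT as everyone randomised and excludes withdrawn subjects from the per-protocol set only. Under Efficacy Analyses, Primary Endpoint, a subject with no end-of-study assessment is counted as an SSI. The analysis set for the primary endpoint is not named.

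**The concern.** Exclusion 7 cannot screen anyone. When a subject is randomised in the operating room, a reoperation has not yet happened. Its only effect, through the removal rule, is to take out randomised subjects because of a later event, and that event may be a consequence of the infection being counted.

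The plan then gives two answers for the same subject:

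- **Disposition rule:** an SSI seen before removal is discarded.
- **Primary-endpoint rule:** a subject removed without an SSI is counted as having one.

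The estimated effect and the power depend on which rule governs. Because the trial is open-label, removal could also differ between arms, and then either rule can produce a spurious difference. If follow-up stops at removal, the day-30 SSI status may not be recoverable at analysis. The conflict between the two rules affects every withdrawal; exclusion 7 is the clearest case.

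**Working it through.** **Inputs from Power and Sample Size:** control SSI 20%; 50% relative reduction (20% v 10%); 300 per group; two-sided chi-square at 5%; 650 enrolled to give 600 evaluable, with about 5% non-evaluable.

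**Assumed:** reoperation and removal rates, because the documents give none.

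**Formula.** With m the mean of p1 and p2, power = Φ{[|p1 − p2| − 1.96·√(2m(1 − m)/n)] / √[p1(1 − p1)/n + p2(1 − p2)/n]}. It is unstratified, as in the plan's own calculation. The planned test is stratified by site, so the figures are approximate.

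**1. Plan's figure.** n = 300, 0.20 v 0.10: (0.10 − 1.96 × 0.02915)/0.02887 = 1.48, so power is 93.1%. This reproduces the 93% in Table 2.1. The calculation uses 300 per group and no missing-as-SSI scoring.

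**2. One basis for the sample size.** 300 evaluable with 5% removed needs 300/0.95 = 316 randomised per arm. Half of 650 is 325, but 325 down to 300 is a 7.7% loss. The dropping rule is therefore shown at 300 analysed, and missing-as-SSI at 316 and 325.

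**3. Formulas for the two rules.** Let r be the share reoperated in an arm, h the share of those infected, and p the true SSI rate.
- Drop (Disposition): (p − rh)/(1 − r)
- Missing-as-SSI (Primary Endpoint): p + r(1 − h)

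**4. True effect present, r = 0.05 in both arms.**

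| Infected among reoperated (control v IrriSept) | Rule | SSI rates | RR | Power |
|---|---|---|---|---|
| 50% v 25% (RR 0.50 holds among them) | Drop | 18.4% v 9.2% | 0.50 | 91% at 300 |
| | Missing-as-SSI | 22.5% v 13.75% | 0.61 | 82% at 316, 83% at 325 |
| 50% v 50% (no effect among them) | Drop | 18.4% v 7.9% | 0.43 | 97% at 300 |
| | Missing-as-SSI | 22.5% v 12.5% | 0.56 | 91% at 316, 92% at 325 |

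At an equal 316 analysed per arm, dropping gives 92% in the first case and 98% in the second, so the gap between the rules is not mainly one of sample size. The second case removes 2.5/20 = 12.5% of control SSIs but 2.5/10 = 25% of IrriSept SSIs. That is why dropping strengthens the effect there and not in the first case.

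**5. No true effect, 20% in both arms.** Let f and g be the shares of SSI and non-SSI subjects removed. Control is given first, and rejection counts both tails.
- Drop, rate p(1 − f)/[p(1 − f) + (1 − p)(1 − g)], 300 per arm, f = 10% v 20%. With g = 0: 18.4% v 16.7%, rejection 8.5%. With g = 5% v 10%: 19.1% v 18.2%, rejection 6.1%.
- Missing-as-SSI, rate p + (1 − p)g, 325 per arm, g = 2% v 4%: 21.6% v 23.2%, rejection 7.8%.
- Equal f and equal g in both arms: 5% under either rule.

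**6. Power after the fix.** 325 per arm, share d with SSI status truly unobtainable and unrelated to SSI, rate p(1 − d) + d:

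| d | SSI rates | Power |
|---|---|---|
| 0 | 20.0% v 10.0% | 95% |
| 2% | 21.6% v 11.8% | 92% |
| 5% | 24.0% v 14.5% | 87% |
| 7.7% | 26.2% v 16.9% | 82% |

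**The case against.** **The primary set is implied.** Scoring missing assessments as SSI has little purpose in a per-protocol set that requires the 30-day visit, so ITT is the natural reading. That stands, but the Disposition sentence is not limited to the per-protocol set, and the 600-evaluable target matches it.

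**The separate SAP can settle it.** It can name the population. It cannot recover outcomes that the protocol stops collecting.

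**Follow-up is not wholly lost.** Follow Up of Patients After Adverse Events continues until resolution, stability, loss to follow-up or withdrawal of consent, and does not list removal by the investigator as a stop. Visit 2 may also be done by telephone or draw on a routine visit. A reader should therefore not infer that all later information disappears. But adverse-event follow-up is not an SSI assessment, and Table 3 schedules that assessment only at Visit 2.

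**Re-entry of the incision is a second exposure.** Interest in wounds that were not reopened is legitimate. That supports a per-protocol or sensitivity set, not removal from follow-up.

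**Stronger readings that the documents do not support.** A reader might infer that dropping reoperated subjects exaggerates the benefit. It does so in the second case of step 4 only because no treatment effect is assumed among them; with the same relative risk there, the RR stays at 0.50 and power falls slightly. A reader might also infer that the false-positive rate is above 5%. That needs removal to differ by arm. The open-label design makes this possible, but no rate or imbalance is documented.

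**Conclusion.** The contradiction is in the text and no other section resolves it. It should be corrected before the first subject is enrolled, because it concerns the sole primary endpoint and outcomes not collected may not be recoverable.

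Its size is unknown. On the assumed 5% reoperated per arm, the choice of rule moves the RR from 0.50 to 0.61 if the treatment effect is the same among reoperated subjects, or from 0.43 to 0.56 if there is none among them. Power differs by about 9 points in the first case (91% v 82%) and 6 in the second (97% v 91%), each at 300 v 316 per arm. Rejection under no effect is 5% with equal removal, and about 6% to 8.5% in the unequal examples. Which arm gains depends on the rule and on the direction of the imbalance.

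The 93% is correct on its own inputs. It does not describe an analysis in which missing assessments are scored as SSI.

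**What to change.** Reconcile the Protocol Synopsis, Exclusion Criteria, Visit 2, adverse-event follow-up, Criteria For Removal, Analysis Populations and Primary Endpoint, and Disposition sections:

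- Limit removal from the study for exclusion criteria to the time before randomisation. Record reoperation within 30 days as a post-randomisation event.
- Follow every randomised subject who has not withdrawn consent to day 30.
- Name ITT with observed SSI status as the primary analysis. Keep any SSI seen before removal, and use missing-as-SSI only where status is unobtainable.
- Do not bar data or replace subjects because of reoperation. Exclusion 7 may stay as the definition of a per-protocol or labelled sensitivity set.
- Report removals by arm and reason.
- State the sample size as a number randomised (Power and Sample Size has 650 enrolled; the Study Summary has about 650 completed), and restate power with the missing rule applied, as in step 6.

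Secondary: exclusions 5 and 6 (damage control laparotomy, drain placement) and the primary-closure criterion, which is confirmed after surgery, may also be settled only after randomisation. State when each is judged relative to randomisation, and follow and report such subjects by arm.

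**Cost.** Protocol wording; one 30-day contact for each subject who would have been dropped; some less typical patients in the primary analysis; and possibly a lower stated power. The change is not free of power cost: at 325 per arm, power exceeds the stated 93% only if almost every status is obtained. Clinical management is unchanged.
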